9.3.3 Secondary Endpoint Analysis

9.3.3.1 D: Self-Selection: Proportion of female selectors who are not breastfeeding at the time of selection decision.

The first secondary endpoint is the proportion in which the denominator includes all females who selected to use the product (regardless of whether they purchased/used) and the numerator includes all female selectors who were not breastfeeding at the time of the selection decision.

9.3.3.2 E: Self-Selection: Proportion of self-selection population who make a correct selection decision regarding use of the product.

This endpoint is the proportion of those subjects making the self-selection decision who make a correct decision about whether the product is right for them to use, as outlined below.

9.3.3.2.1 Populating the Self-Selection Table

Each subject will be classified on two key variables: (1) the selection decision and (2) the appropriateness of use given the selection decision, in order to populate the typical 2x2 self-selection table.

Selection Decision: The selection phase of the interview consists of the self-selection and purchase questions, with accompanying neutral follow-up questions. All subjects who go on to actually purchase the study product will be categorized as selectors. Even

subjects who do not eventually complete the purchase of the product will be classified as a selector or a non-selector primarily on the basis of the initial self-selection and purchase questions, or in the case of a positive enrollment pregnancy result, the second self-selection and purchase question. However, all information recorded during the selection phase of the interview will be considered in the classification of subjects as selectors or non-selectors. Subjects who offer modifying information in open-ended responses to neutral probing will be re-categorized accordingly.

Appropriate to Use:

Non-selectors will be classified on the variable Appropriate for Use as follows:

Yes: meets the label criteria for use, representing those who could have selected appropriately, but did not (**Cell C**).

No: does not meet the label requirements for use, and appropriately did not select (**Cell D**). This includes those subjects who otherwise might have met the strict criteria for appropriate use according to the DFL, but who give a medically appropriate rationale for their non-selection decision. For example, if a subject who otherwise meets the labeled criteria for use does not select the product and cites the fact that they are taking a medicine for Human Immunodeficiency Virus (HIV) as their reason for not selecting (which otherwise does not disqualify a subject from using, but rather suggests that they talk to a doctor), that subject will be re-classified from Cell C to Cell D. A physician will review the casebook for each subject who falls into Cell C to determine if any subjects meet that criterion.

Selectors will be classified on the variable Appropriate for Use as follows:

Yes: either meets the strict label criteria for use (1-Correct Selectors) or reported and measured characteristics justify the selection decision (2-Acceptable Selectors), representing those who chose to use the product who made a clinically acceptable decision despite not meeting the strict label criteria for use (**Cell A**).

No: does not meet strict label criteria and reported and measured characteristics do not justify the selection decision (3-Incorrect Selectors), representing those who chose to use the product, but should not have (**Cell B**).

Complete definitions of Correct, Acceptable, and Incorrect Selectors follow:

- 4) Correct Selectors. Subject meets the strict criteria of the Drug Facts label, including:
 - a) No contraindications (not pregnant or breastfeeding, no known allergy to any of the ingredients, no previous use of ella® within the same menstrual cycle, no use as regular birth control)
 - b) Is a woman of childbearing potential. This would include all women who do not report any of the following: surgical sterilization (tubal ligation, hysterectomy, or bilateral oophorectomy) or postmenopausal for at least one year
 - c) Has had unprotected sex in the 5 days prior to use of the product

- 5) Acceptable Selectors. Subject does not meet the strict criteria of the Drug Facts label, but selection is classified as appropriate because they are judged clinically (see Section 8.4.3) to be an appropriate selector. This group is expected to be quite small.
- 6) Incorrect Selectors. This group includes selectors who are not correct or acceptable, including having any of the following:
 - a) A contraindication to the product (are pregnant or breastfeeding, has an allergy to one of the ingredients, previously used ella® within the same menstrual cycle, or use as regular birth control)
 - b) Is a man
 - c) Is a woman without childbearing potential. This would include all women who report any of the following: surgical sterilization (tubal ligation, hysterectomy, or bilateral oophorectomy) or postmenopausal for at least one year
 - d) Has not had unprotected sex in the 5 days prior to use of the product

This secondary endpoint is the proportion in which the denominator includes all dosing instances of the IP among those who start or restart hormonal contraception in the same menstrual cycle and the numerator includes dosing instances where the subject reports using condoms every time they have sex during the remainder of that menstrual period.

9.3.3.5 H: Actual Use: Proportion of user population who do not use the study product more than once in the same menstrual cycle.

This secondary endpoint is the proportion in which the denominator includes all subjects who take at least one dose of the product (user population) and the numerator includes all subjects who do not use more than one dose(s) of the study product within the same menstrual cycle after taking the initial dose of ella®.

9.3.3.6 I: Self-Selection/Actual Use: Proportion of self-selection population taking one of the “ask a doctor or pharmacist before use” products who do not select, who select but do not use or who report contacting a healthcare provider or pharmacist.

This secondary endpoint is the proportion defined by the denominator including all subjects who participate in the self-selection interview who report taking one of the “ask a doctor or pharmacists before use” compounds (including barbiturates, carbamazepine, felbamate, oxcarbazepine, phenytoin, topiramate, rifampin, griseofulvin, a prescription drug to treat HIV/AIDS, bosentan, or a supplement containing St. John’s Wort) and the numerator is all such subjects who either do not select or use or who report talking with a doctor or pharmacist about it use during the course of the study.

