	
25 women's health clinics and 10 retail pharmacy research sites.
 
In order to be as representative as possible of the OTC EC-seeking population, when potential subjects come to a site looking to purchase EC, they will be offered the opportunity to participate in the study. Potential subjects will be directed to study staff for a face-to-face interview and screened for initial study inclusion criteria.
 
Subjects who meet the initial screening inclusion criteria for the study will be given an (empty) ella® package and will be allowed as much time as they need to review the information on the outside of the entire package. Subjects will be asked to make a selection decision regarding whether the product is appropriate for them to use or not. Reasons for selection and deselection will be recorded. Those that select the product will then be told the cost of the investigational product and will be asked if they would like to purchase it for their own use. Reasons for any non-purchase and purchase decisions will be recorded.
 
Following the purchase decision, subjects will provide demographic information and limited medical history. The Rapid Estimate of Adult Literacy in Medicine (REALM)¹ or Rapid Estimate of Adolescent Literacy in Medicine (REALM-Teen)² will then be administered. Subjects will be asked to sign the informed consent and then provide information about current medication use. Subjects who sign consent will provide a urine sample for pregnancy testing. Subjects with a positive pregnancy test result will be informed that the test was positive, will be asked the selection and purchase question again to better assess their self-selection decision, and then excluded from further study participation. Qualified subjects will be allowed to purchase the study product and told they may return to the site at any time to resupply. Subjects will not be allowed to purchase more than 3 one-dose packages at a time or more than 9 one-dose packages during the study period (although this will not be communicated to the subjects unless they attempt to purchase more than that). While any request for more will be denied, the request will be recorded.
 
Subsequent contact will be by up to two telephone interviews conducted by trained nurses (interviewers) at a central research site. Subjects will be contacted by phone at Week-2 (Day 14 with an allowable window of ± 3 days) and at Week-6 (Day 42± 4 days) to gather information on if, how and when the subject took the product, any adverse events (AEs), concomitant medications, and other actions the subject may have taken related to the use of the product. Results of the End-of-Study pregnancy test will be reported by subjects and recorded.
 
Once all steps of the final telephone interview are completed, the subject will be instructed to return leftover study medication, if any, and empty packaging to PEGUS and will exit the study.

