The schedule of activities table provides an overview of the protocol visits and procedures. Refer to the STUDY PROCEDURES and ASSESSMENTS sections of the protocol for detailed information on each procedure and assessment required for compliance with the protocol. The investigator may schedule visits (unplanned visits) in addition to those listed on the schedule of activities, in order to conduct evaluations or assessments required to protect the well-being of the subject.

Visit Procedure	Intercept Recruitment	Enrollment Visit / First Purchase ^a	Week 2	Week 6	End of Study / Early Termination ^e
		Day 1	14±3 Days	42±4 Days	
Invitation to participate	X				
Review screening / study inclusion criteria		X			
Subject reviews outer packaging and makes selection and purchase decision		X			
Collect demographics and relevant medical history		X			
Administer REALM or REALM-Teen test ^c		X			
Study exclusion/inclusion criteria assessed for eligibility to continue		X			
Subject signs informed consent		X			
Urine pregnancy test performed ^h		X			
Collect current/regular relevant medications and associated conditions ^b		X			
Purchase transaction conducted ^d		X			
Telephone interviews			X	X	X
End-of-study telephone interview					X
Record End-of-study pregnancy test results ^f					X
Concomitant medications		X	→	→	X
Adverse Events		X	→	→	X
Reimbursement for cost of study medication (After all subjects complete the study) ^g					X

Abbreviations: → = ongoing/continuous event; REALM = Rapid Estimate of Adult Literacy in Medicine; REALM-Teen = Rapid Estimate of Adolescent Literacy in Medicine

- a. Day relative to first purchase of study medication (Day 1).
- b. Subjects will be asked to provide a list of any conditions they have and any medications they are taking. Females only.
- c. REALM or REALM-Teen will be conducted for all subjects who participate in the enrollment interview regardless of self-selection/purchase decision.
- d. Subjects will be allowed to purchase any amount of study medication up to 3 packages at the baseline visit, or return to the site at any time during their use phase and purchase the maximum amount (up to 9 packages) allowed during subsequent treatment weeks (6 weeks).
- e. Early termination interview will be conducted during the study if the subject is discontinued or withdraws consent prior to Week 6.
- f. Subjects are provided with a urine pregnancy test at enrollment and asked to keep it until directed to use it at the end of study.

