5.2.2 After Purchase Decision and Before Use Phase

The purpose of this study is to see how the subject complies with the labeled directions; therefore, the date of the use of study medication is determined by the subject. Study Day 1 will be defined as the day the product is dispensed to the subject. On Study Day 1, subjects will complete the enrollment interview including associated medical conditions and demographic information. Subjects will also be asked to complete the REALM¹ or REALM-Teen² test to establish reading ability.

Study exclusion criteria will be assessed and only qualified subjects who decide to purchase the product will continue on to the study use phase. Subjects will provide informed consent. Parental consent and subject assent will be obtained where required based on applicable local laws and regulations. See Section 12.3 for further information on parental consent of adolescent subjects.

After consent, all subjects will provide a urine sample for the study staff member to conduct a urine-based dip pregnancy test. Subjects with a positive pregnancy test will be asked to make a selection and purchase decision again with the new information regarding pregnancy and then excluded from the use phase of the study.

Qualified subjects will be required to provide contact information (for the purposes of conducting telephone follow-up interviews) and information regarding any medications they are currently using. Subjects who choose to will then purchase the IP and site study staff will complete the electronic product accountability form. While it is expected that most subjects will purchase a single package of ella®, subjects will be allowed to purchase up to 3 boxes in any one day, and will be allowed to return to the study site at any time during the use phase to purchase additional medication. Subjects will not be allowed to purchase more than 3 single dose packages in a single day, or more than 9 single-dose packages during the study period although this will not be communicated to the subjects unless they attempt to purchase more than that. Any requests for purchase more than the limits will be recorded.

Subjects will also be informed that study and End-of-Study (EOS) phone interviews will be conducted at Week 2/Day 14 (with an allowable window of ± 3 days) and at Week 6/Day 42 (± 4 days). Subjects who have purchased the product will be dispensed the product to use how and when they see fit.

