9.2 Analysis Populations

The populations of interests are defined as follows:

- Responder Population: Subjects who accept the invitation to participate and begin the screening process (including those who do not meet screening criteria for proceeding to the self-selection phase).
- Self-Selection Population: Subjects who accept the invitation to participate and meet study inclusion criteria, participate in a face-to-face interview at the study site and make a self-selection and purchase decision.
- Purchasers: Subjects who meet study enrollment criteria and purchase the study medication.
- User Population: Subjects who take at least one dose of study medication during the study.
- Recent hormonal contraceptive users: Subjects in the user population who also report recent hormonal contraceptive use (i.e., use of a hormonal contraceptive within the previous two months).

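### The protocol gives conflicting instructions on who is asked about current medicines, so the data source for part of secondary Endpoint I is not secured

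*Protocol*

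**What the plan says.** Endpoint I (Section 9.3.3.6) is a proportion with "the denominator including all subjects who participate in the self-selection interview who report taking one of the" medicines on the ask-first list. A subject is a success if she does not select, does not use, or reports speaking with a doctor or pharmacist. Section 9.2 fixes the self-selection population as those who meet the inclusion criteria, "participate in a face-to-face interview at the study site and make a self-selection and purchase decision". Neither consent nor purchase is required.

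On when medicines are asked about, and of whom, the protocol says several things:

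- **Protocol Summary, Methods:** "Following the purchase decision, subjects will provide demographic information and limited medical history". The reading test comes next, and then: "Subjects will be asked to sign the informed consent and then provide information about current medication use".
- **Schedule of Activities:** the medication row stands after the eligibility, consent and urine-test rows. Its footnote b reads "Subjects will be asked to provide a list of any conditions they have and any medications they are taking", and restricts this to females. Footnote c says that the reading test "will be conducted for all subjects who participate in the enrollment interview regardless of self-selection/purchase decision". Footnote b has no such wording.
- **Section 5.2.2:** "only qualified subjects who decide to purchase the product will continue on to the study use phase". After consent and the urine test it continues: "Qualified subjects will be required to provide contact information (for the purposes of conducting telephone follow-up interviews) and information regarding any medications they are" using.
- **Sections 4.5 and 6.2:** Section 4.5 has a medication question at enrollment. Section 6.2 has a short medication history after the selection and purchase decisions. Neither is limited to subjects who consent or qualify.
- **Section 12.3:** no PHI is to be collected from subjects who fail screening, do not qualify or do not sign. The next sentence keeps, as anonymous study data, whatever is collected after explicit permission. Later in the section, verbal permission must come before any health question.

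**The concern.** The endpoint needs medication data from women who stop at the selection or purchase decision, because their stopping is what two of its three routes to success count. One set of instructions would not obtain those data; another would. The protocol does not say which governs.

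If the post-consent sequence is built into the questionnaire, the women left out are not a neutral loss: every one of them would have been a success. Section 3.5 provides for a standardized questionnaire, so the choice is made once for the whole study. A SAP can redefine a denominator, but it cannot recover answers that were never requested. Endpoint I was added after FDA comments, according to the amendment history, so it is likely to be read closely.

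**Working it through.** **1. Who is needed and who is asked.** For a woman on a listed medicine:

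| Group in the self-selection population | Result under 9.3.3.6 | Asked under the summary and 5.2.2 sequence? | Asked under 4.5 and 6.2? |
|---|---|---|---|
| Non-selector at the first decision | Success | No | Yes |
| Selector who declines purchase or consent | Success (cannot use) | No | Yes |
| Selector disqualified before consent | Success (cannot use) | No | Yes |
| Consents, urine test positive | Success (excluded from use) | Summary: yes, medicines come before the test. 5.2.2: not as a qualified subject | Yes |
| Purchaser | Depends on use and on contact | Yes | Yes |

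Under the post-consent sequence the first three groups enter only if a woman volunteers her medicine, as in the HIV example in Section 9.3.3.2.1. The phrase about subjects who report a medicine does not solve this: a woman who is not asked can report only by volunteering.

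**2. Direction.** Let a be the number asked, s the successes among them, o the number not asked (all successes), and v those of the o who volunteer.

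- Observed = (s + v)/(a + v)
- Defined = (s + o)/(a + o)

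Since v ≤ o and s ≤ a, observed never exceeds defined. With assumed counts a = 20, s = 8, o = 5:

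- none volunteer: 8/20 = 40%
- two volunteer: 10/22 = 45%
- all five asked: 13/25 = 52%

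**3. Ceiling on the size.** The only relevant count is in Section 9.1: up to 1270 interviewed for 950 purchasers, at a 75% yield. Check: 950/0.75 = 1266.7, which agrees with the stated figure.

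- Not proceeding: 1270 − 950 = 320, and 320/1270 = 25.2%.
- Assume listed medicines are equally common among the 950 and the 320, that none of the 320 is asked, and that none volunteers. Let p be the proportion of successes among those asked.
- Defined value = (950p + 320)/1270.
- Shortfall = (950p + 320)/1270 − p = (1 − p) × 320/1270 = (1 − p) × 25.2 points.

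| p (assumed) | Defined value, at most | Shortfall, at most |
|---|---|---|
| 20% | 40% | 20 points |
| 40% | 55% | 15 points |
| 60% | 70% | 10 points |
| 80% | 85% | 5 points |

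This is a ceiling because the 320 include screen failures, who are outside the self-selection population, and may include women who were asked but did not purchase. The shortfall is zero if no woman on a listed medicine goes unasked. It can exceed the ceiling only if women on listed medicines drop out more often than others.

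**The case against.** A reader might infer that medicines are asked only of qualified subjects and that non-selection has no systematic data source at all. The documents do not support that:

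- The Schedule sends the reader to both the procedures and the assessments sections for detail. Section 6.2 is an assessments section, and its medication history is not limited to consenters. Section 4.5 is equally general. Section 5.2.2 says what qualified subjects must provide; it does not say that others are not asked.
- Footnote b's restriction to females would be redundant if only qualified subjects were asked, because men are already excluded from the use phase (Section 3.3.2). It suggests a wider group.
- Row order is weak evidence. The Schedule puts the urine test before medicines and the summary puts it after.
- Under the summary's order, a woman with a positive urine test has already given her medicines. She is then asked to select again and may become a non-selector, so that limb is not strictly empty.
- Placing non-selectors in Cells C and D relies on self-reported medical information (Section 8.3), so the no-PHI sentence cannot sensibly bar every anonymous health answer.
- The questionnaire and the flow chart are not in the text at hand and may settle the matter.

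All of this stands against the absolute reading. It does not remove the conflict. The summary, the Schedule and Section 5.2.2 all put the question after consent. The Cell C and D classification shows that some health data are taken from non-selectors, but listed medicines are not among its label criteria, so it does not show that medicines are asked.

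One further objection bears on the remedy. Table 1 takes this message from the leaflet, which is inside the package, while subjects see only the outer package when they select (Sections 3.1 and 3.6). Non-selectors therefore become successes without having read the message. That stands and is reflected in the fix.

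**Conclusion.** The point holds as a contradiction about who is asked, not as a proven absence of data. If the summary and Section 5.2.2 are followed, most non-selectors, and selectors who stop before the question, are missed unless they volunteer, and Endpoint I can only come out too low. The direction follows from the definition alone.

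The size does not follow from the documents, which give neither the prevalence of listed medicines nor the number of non-selectors. The bound of (1 − p) × 25.2 points rests on equal prevalence and on treating all 320 as unasked members of the population. Reading the 5 to 20 points as an expected bias would go too far: Section 9.1 itself expects most who enter the self-selection phase to purchase.

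Endpoint I is secondary and has no threshold (Section 9.3.2 sets thresholds only for A, B and C), so the primary conclusions are untouched. The conflict should still be resolved before the questionnaire is fixed, because it cannot be repaired afterwards.

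**What to change.** Reconcile the Methods summary, the Schedule of Activities and Sections 4.5, 5.2.2, 6.2, 9.3.3.6 and 12.3.

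**Preferred.** State that the open medication question is put to every female self-selection participant after the selection and purchase questions, under the verbal permission and anonymous retention already in Section 12.3. Reword the no-PHI sentence so that it plainly allows this anonymous item. Report the contribution of non-selectors to Endpoint I separately, since they have not seen the leaflet message when they decide. The cost is one question moved earlier, one sentence clarified, and a slightly longer interview for subjects who do not proceed. Purchasers are asked already, and the question comes after the selection decision, so it cannot influence that decision.

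**Otherwise.** Define the Endpoint I denominator as the subjects actually asked, and say in Sections 2.2.2, 2.3 and 9.3.3.6 that it no longer covers the whole self-selection population. Any non-selection limb then covers only non-selectors who were asked, such as women who change their decision after a positive urine test. The cost is a narrower endpoint that says little about selection.
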